## Sex Effects on Blood Pressure With Handgrip Training

### Research protocol

This study will be designed as a randomized, controlled, cross-over, repeated measures experiment. Fifty young healthy adult participants (25 males and 25 females) will visit the laboratory three times to perform a fatiguing bout of isometric handgrip exercise before and after both 4 weeks of isometric handgrip training and a no-exercise training condition. Participants will be randomly allocated to the isometric handgrip and the non-exercise training conditions using an online program (<http://www.randomizer.org/>). Participants that start with isometric handgrip training will return to the laboratory after a 4-wk washout, as this duration has been shown to decondition cardiovascular outcomes following training (1–3). To eliminate diurnal variation, each participant will visit the laboratory at the same time of day. Main outcomes in each visit will be measured at rest, during the fatiguing bout of isometric handgrip exercise, and 5, 10, 30, and 60-min post-exercise (see figure and Table 1). These measurement timings are aimed to characterize BP, and the cardiac autonomic and vascular function biphasic responses (4–6). Visits 2 and 3 will take place within 7 days of the last training session.

**Figure 1:** Experimental design, a randomized, controlled, cross-over, repeated measurements study. Abbreviations: CON; control, BRS baroreflex sensitivity, RMSSD, root mean square of

**Table 1** Procedures to be conducted in each visit to the laboratory

Procedures	Time (min)
Rest	15
Measurements	
1) BP, arterial stiffness, cardiac autonomic function	5
2) Brachial endothelial function (FMD)	15
Fatiguing isometric handgrip exercise	~ 3-5
Last isometric contraction	
Measurements	
1) BP, brachial blood flow	
2) Cardiac autonomic function (BRS, RMSSD, HF)	
Post 5 min	
Measurements	
1) BP, arterial stiffness (cfPWV), cardiac autonomic function (BRS, RMSSD, HF)	5
Post 10 min	
Measurements	
1) Brachial endothelial function (FMD)	15
Post 30 min	
Measurements	
1) BP, arterial stiffness (cfPWV), cardiac autonomic function (BRS, RMSSD, HF)	5
2) Brachial endothelial function (FMD)	15
Post 60 min	
Measurements	
1) BP, arterial stiffness (cfPWV), cardiac autonomic function	5
2) Brachial endothelial function (FMD)	15
	Total ~ 100

successive differences; HF, high-frequency power band; FMD; brachial artery flow-mediated dilation, cfPWV; central pulse wave velocity.

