## Study intervention

### Baseline visit – fatiguing bout of Isometric handgrip exercise

All participants will rest for 15-min, and then the MVC will be determined based on three attempts, each separated by 30-s, with participants in a supine position. The highest MVC will be used to define the exercise workload (30% MVC). Then, participants will perform a fatiguing bout of unilateral isometric handgrip exercise in the supine position using a digital handgrip transducer intertwined with a data acquisition system (Powerlab 16/35; ADInstruments, BellaVista, NSW, Australia). Participants will use their dominant hand and will hold the isometric contraction until task failure. The failure criteria will be defined as the inability to sustain the contraction force within 5% of the target MCV percentage (i.e., 30%). We chose to set the intensity at 30% MVC as this is the standard target intensity of isometric handgrip exercise protocols (7–9) and no differential BP responses have been reported when different intensities (i.e., 20 vs 30 and 45% MVC) are

used (10–12). Based on previous research, we expect that participants will fatigue within 3 to 5 min (i.e., time to task failure) (12). Participants will receive both visual and auditory feedback to maintain the target exercise intensity throughout the session. The same fatiguing bout protocol will be used before and after the training intervention.

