#### Isometric handgrip training intervention and control

Participants will train three days per week at home for 1 month using a reliable and validated digital handgrip dynamometer (DynX, MD System, Inc., Westerville, OH, USA)) in a seated position. The isometric handgrip training protocol will consist of four sets (2 for each hand) of two-min sustained contractions starting at 30% MVC interspersed by 1-min resting periods (a total of 12-min). All training sessions will be remotely supervised via Zoom or phone call by a research team member to ensure compliance with the exercise prescription. Before each training session, MVCs will be re-assessed over three repetitions, each separated by 30-s, to ensure an accurate exercise prescription (13). The highest value will be used to determine the target intensity of the session. In the control/washout conditions, participants will be instructed to maintain their normal daily routines.

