#### Post-intervention visits – isometric handgrip exercise acute bout

All participants will return to laboratory to complete the same acute bout of isometric handgrip exercise detailed in the baseline visit after the isometric handgrip exercise training and respective control.

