### Statistical analysis

Linear mixed models will be used to examine the effects of acute isometric handgrip exercise and training on BP, cardiac autonomic, and vascular function outcomes over time (i.e., aim 1, 2, and 3). These will be fitted with restricted maximum likelihood and applying Satterthwaite's method for approximating degrees of freedom for the F test using R lmerTest package (32). Fixed effects will be set as time, sex, training condition, and the random intercept as each participant. All models' residuals will be checked for normality and homogeneity of

variances using both Shapiro-Wilk and Levene tests, respectively, and through QQ plot inspection using the R performance package (33). Natural logarithm (Ln) transformations will be applied to HRV outcomes, as these are generally not normally distributed, but both transformed and untransformed data will be presented. Linear mixed models will be run with and without possible outliers identified through box plots as observations lying outside the 1.5 interquartile range. Unbiased effect sizes - partial omega squares ( $\omega^2$ ) will be estimated for each fixed effect and interactions terms and interpreted accordingly to the rough benchmarks set by Cohen (34) [small ( $\omega^2 < 0.05$ ), medium ( $\omega^2 < 0.25$ ), and large ( $\omega^2 > 0.25$ ) effects sizes]. Post-hoc comparisons will be performed using the Bonferroni correction, in the presence of significant fixed effects and interactions. MVC, %fat and free fat mass, and physical activity outcomes will be added to all linear mixed models as covariates, whereas resting HR and SRauc will be added to FMD and HRV main outcomes, respectively. In addition, the repeated measures correlation coefficient will be used to test associations between isometric handgrip exercise-induced BP changes before and after the training intervention and of BP with cardiac autonomic and vascular function outcomes (35). Multiple imputation procedures using full information maximum likelihood will only be used in case of a significant amount of missing data on outcomes (>15%) and if missing completely at random, as linear mixed modeling provides robust estimates for small to medium amounts of missingness (36). All statistical analyses will be conducted using R software, version 4.2.3 (37) with a significant level ( $\alpha$ ) of 0.05.

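### The cross-over model has no period term, so a visit 2-to-3 shift can leak into the training and sex x training effects; separately, the 7-day visit rule conflicts with the 4-week washout

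*Combined protocol and SAP*

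**What the plan says.** The Research protocol describes a randomised cross-over in which 50 adults (25 per sex) attend three visits, "before and after both 4 weeks of isometric handgrip training and a no-exercise training condition". Allocation is described only as: "Participants will be randomly allocated to the isometric handgrip and the non-exercise training conditions using an online program". No blocking or stratification by sex is stated.

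One section is headed "Baseline visit – fatiguing bout of Isometric handgrip exercise". The section on post-intervention visits then has participants return to "complete the same acute bout of isometric handgrip exercise detailed in the baseline visit after the isometric handgrip exercise training and respective control". Together these point to one common baseline (visit 1) and one visit after each condition.

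The model in Statistical analysis is: "Fixed effects will be set as time, sex, training condition, and the random intercept as each participant". Interactions are mentioned but not listed. No period, visit or sequence term appears, and the levels of training condition are not given.

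On timing, the Research protocol says both "Participants that start with isometric handgrip training will return to the laboratory after a 4-wk washout" and "Visits 2 and 3 will take place within 7 days of the last training session". The training section adds: "In the control/washout conditions, participants will be instructed to maintain their normal daily routines".

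**The concern.** Within each participant, the training effect is a comparison of visit 2 with visit 3, in one order or the other. Anything that moves the outcome between those visits, such as familiarisation, season or equipment drift, is separated from training only by balanced sequences or a period term. The plan guarantees neither.

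The model also has only a participant intercept, so it treats every reading within a visit as independent information. A visit-wide shift moves all of them together, and the standard error understates the uncertainty it causes. At stake are false-positive claims for the training main effect and for sex x training, the contrast that the trial's title points to.

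The timing sentences are a separate matter: as worded, they cannot all be followed.

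**Working it through.** **Inputs from the documents.** 50 participants, 25 per sex, three visits (Research protocol). Five blood pressure time-points per visit: rest, last contraction, and 5, 30 and 60 min (Table 1). Model terms (Statistical analysis). Target difference 5 mmHg and alpha 0.05 (Sample size).

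**Assumptions; the documents give no figures.** Visit 2-to-3 shift h of 3 or 5 mmHg; residual SD s of 3 or 5 mmHg; simple randomisation; no true effect; no other visit-level noise. Time is read as the within-visit time-points, and visit 1 is its own level.

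**1. The leak.** Post-training minus post-control picks up -h in a train-first participant and +h in a control-first participant. The average is

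leak = h x (n control-first - n train-first)/n.

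With 20 train-first and 30 control-first: 3 x 10/50 = 0.6 mmHg, or 5 x 10/50 = 1.0 mmHg. A 20/30 or worse split, in either direction, has probability 0.20. Over all randomisations the leak has mean zero. Its mean absolute size at h = 3 and 5 is 0.34 and 0.56 mmHg for the main effect, and 0.67 and 1.12 mmHg for sex x training.

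**2. What the model allows for.**
- Actual variance of the contrast = (2s²/5 + h²)/50.
- Model variance = 2σ²/(5 x 50). Here σ² is s² plus the part of the shift that falls into the residual. Once condition means are removed, the ten readings at visits 2 and 3 deviate by about h/2, giving 10 x h²/4 = 2.5h² per participant over about 14 df, so σ² = s² + 0.179h².
- Type I error = 2 x [1 - Φ(1.96/ratio)], where ratio = actual SD / model SE.

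| s | h | Actual variance | Model variance | Ratio | Type I, formula | Type I, simulation |
|---|---|---|---|---|---|---|
| 5 | 3 | (10 + 9)/50 = 0.380 | 2 x 26.61/250 = 0.213 | 1.34 | 14% | about 14% |
| 5 | 5 | (10 + 25)/50 = 0.700 | 2 x 29.46/250 = 0.236 | 1.72 | 26% | about 25% |
| 3 | 3 | (3.6 + 9)/50 = 0.252 | 2 x 10.61/250 = 0.085 | 1.72 | 26% | about 25% |
| 3 | 5 | (3.6 + 25)/50 = 0.572 | 2 x 13.46/250 = 0.108 | 2.30 | 40% | 39 to 41% |

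For sex x training both variances are multiplied by 4 (1/25 + 1/25 = 4/50), so the ratios and error rates are about the same.

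With a period term the shift leaves both the contrast and the residual, and simulated type I error is about 5%. With exactly balanced sequences and no period term the leak is zero and type I error is at or below 5%. For example, at s = 5, h = 3: √(0.200/0.213) = 0.97, giving about 4%.

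**3. One value per visit.** Actual variance is (2s² + h²)/50 and model variance (2s² + h²/2)/50. The numerators are 59 against 54.5 (s = 5, h = 3), 75 against 62.5 (s = 5, h = 5), 27 against 22.5 (s = 3, h = 3) and 43 against 30.5 (s = 3, h = 5). Type I error is about 6 to 10%.

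**4. Time x training.** (post + h) - (rest + h) = post - rest. A shift common to all time-points cancels.

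**5. What a period term does not do.**
- *Carry-over.* If a fraction c of the effect T is retained, train-first participants contribute T - cT and control-first participants T. The average is T(1 - c/2): 0.875T at c = 0.25 and 0.75T at c = 0.5.
- *Random visit-to-visit variation.* With visit SD 3, s = 5 and no shift, actual variance is 2(9 + 25/5)/50 = 0.560. The visit deviations add 5 x 2 x 9/14 = 6.43 to the residual, so model variance is 2 x 31.43/250 = 0.251. The ratio is 1.49 and type I error about 19%, with or without a period term.

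**6. Visit timing against the 7-day rule.**

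| Sequence | Visit 2 | Visit 3 |
|---|---|---|
| Train-first | can be met | follows a 4-week washout, so at least 28 days after the last session |
| Control-first | no earlier training session exists | can be met |

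Read literally, the rule fails in two of four cells.

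**The case against.** The best defence is that omitting period does not bias a balanced cross-over, and that over randomisations the leak averages zero even without balance. That stands: there is no systematic bias, and the harm is understated uncertainty.

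The shifts are assumed, and 5 mmHg equals the trial's whole target difference. Same-time-of-day visits, a 15-minute rest and averaged readings should limit them. That also stands, so the percentages are illustrations, not predictions. They also assume no other visit-level noise. With visit SD 3, s = 5 and h = 3, actual variance without period is (28 + 9)/50 = 0.740 against a model variance of 2 x 33.04/250 = 0.264. Type I error is then about 24%, against about 19% with period, so the missing term is only part of the problem.

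A paired analysis of visit 2-to-3 differences would hold type I error near 5% without a period term, because the shift would enter its variance estimate. That is not the planned model.

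One could say that time means visit order. The model would then have no term for the within-visit time-points that the protocol sets out to characterise.

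A reader might infer stronger faults: that visit 1 is pooled with post-control, or that visit 2 serves as the control baseline for train-first participants. Either would bias the estimate, but the plan states neither, and its baseline and post-intervention sections point to one common baseline. A reader might also infer that the acute-response aim is compromised; a common shift cancels from those contrasts.

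The 7-day sentence may be meant to run from the end of each condition. That would remove the conflict, but the text refers to the last training session.

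**Conclusion.** The concern holds in limited form. The model omits period, and the plan states no balancing of sequences, so a visit 2-to-3 shift can inflate type I error for the training main effect and sex x training. Under the stated assumptions the range is about 14% to 40% with five readings per visit, and about 6 to 10% with one. It is about 5% with a period term, and there is no inflation from this source if sequences are balanced. The size depends on the assumed shift, residual SD and simple randomisation, and on visit 1 being its own level. Time x training contrasts are untouched by a common shift. The documents do not support a claim of systematic bias.

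The timing conflict follows from the wording alone and needs no assumption about size. The visit order is inferred from the text, because Figure 1 is not reproduced.

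**What to change.** In Statistical analysis:

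1. Code training condition with three levels (baseline visit 1, post-control, post-training) and define the training effect as post-training versus post-control.
2. Add period (visit 2 versus 3) as a fixed effect, and period x sex to protect the sex x training contrast.
3. State that period does not remove carry-over. Add a participant-by-visit random intercept, since period alone does not cure inflation from random visit-to-visit variation.

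In the Research protocol, the sponsor should reconcile the 7-day sentence with the 4-week washout and with the control-first sequence. No timing is proposed here.

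The cost is wording only, with no extra visits, measurements or participants. The third condition level, period and period x sex take one degree of freedom each. If there is no shift, period raises the standard error by about 1%: chance imbalance multiplies the variance by about 1.02, and √1.02 is about 1.01. Period x sex adds about 1% more.

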### *Cardiac autonomic function*

We will place electrodes directly on the skin of each participant to obtain the ECG trace required to estimate both heart-rate variability and baroreflex sensitivity outcomes.

**Heart rate variability and baroreflex sensitivity:** R-R intervals will be sampled at 1000 Hz frequency to obtain digital R waves digital sequences using the single ECG lead module of PowerLab data acquisition system (ADInstruments, BellaVista, NSW, Australia). All data acquisition and offline analyses will be conducted following the standards of the Task Force of the European Society of Cardiology and the North American Society of Pacing and Electrophysiology (17). Offline heart rate variability (HRV) analyses will be performed over a 2-min time series for each time-point (i.e., baseline, during and 5, 30 and 60 min after exercise) using the HRV analysis module of Lab Chart 8 (ADInstruments, BellaVista, NSW, Australia) (18). Main time-domain indices of interest include the standard deviation of NN intervals (SDNN) – a measure of overall variability, and the root mean square of the sum of the squares of the differences between NN intervals (RMSSD) – a measure of cardiovagal modulation. In addition, non-linear time-domain parameters will be derived from the Poincaré plot, including the vertical deviation that reflects mainly cardiovagal modulation (SD1), the longitudinal deviation (SD2), and the non-linear ratio SD1/SD2 an index of autonomic balance analogous to LF/HF ratio (19). The time-frequency domain analysis will be conducted using the Lomb-Scargle Periodogram, which permits accurate estimation of low (0.04 to 0.15 Hz) and high-power frequency (HF) power bands (0.15 to 0.40 Hz) in absolute and normalized power units during exercise conditions. Cardiac baroreflex sensitivity (BRS) will be estimated via the spontaneous sequence method over 2 min through the Lab Chart 8 baroreflex macro. Briefly, this method identifies ramps where increases in SBP ( $> 1$  mmHg) are coupled with increases of the RR interval ( $> 4$  ms) (linearly correlated) that occur over at least 3 beats (minimum sequence). The minimum acceptable correlation coefficient between SBP and RR interval ramps will be 0.80. Then, baroreflex sensitivity is estimated as the average of all regression slopes between the SBP and RR interval.

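### For outcomes read during the fatiguing contraction, the planned mixed model forces one residual variance on rest, task failure and recovery, and no action follows if the homogeneity check fails

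*Combined protocol and SAP*

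**What the plan says.** The Statistical analysis section gives the model in full: "Fixed effects will be set as time, sex, training condition, and the random intercept as each participant". It is fitted by REML, with Satterthwaite's method for "approximating degrees of freedom for the F test using R lmerTest package". No variance function, further random effect, structured covariance or robust standard error is named.

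Residuals are to be checked for normality and equal variance "using both Shapiro-Wilk and Levene tests, respectively", plus QQ plots. Nothing is said about what happens if the variance check fails. Two related provisions exist: "Natural logarithm (Ln) transformations will be applied to HRV outcomes, as these are generally not normally distributed", and "Linear mixed models will be run with and without possible outliers identified through box plots". Post-hoc comparisons are Bonferroni-corrected and made only after a significant effect or interaction.

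The Research protocol section has the main outcomes "measured at rest, during the fatiguing bout of isometric handgrip exercise, and 5, 10, 30, and 60-min post-exercise". Table 1 narrows this. At the last contraction it lists BP, brachial blood flow, BRS, RMSSD and HF, but neither FMD nor cfPWV. The Cardiac autonomic function section confirms a 2-minute HRV series "for each time-point (i.e., baseline, during and 5, 30 and 60 min after exercise". In the Blood pressure section the arm cuff is used only before and after exercise, so BP during the contraction comes from the finger device.

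**The concern.** One of the five BP and autonomic readings per visit is taken at the end of a contraction held to failure; the others are taken at supine rest or in recovery. Nothing in the design makes equal residual spread across these states likely, yet the model assumes it. Every standard error at every time point is then built from one averaged variance. If the exercise reading is the noisier one, it inflates the standard errors at rest and in recovery, where a training-induced fall in pressure would be looked for, and the exercise standard error can be too small. This is separate from correlation between readings of the same visit: it would remain if those readings were independent.

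**Working it through.** The plan gives no figure on this point to reproduce, and the sample-size statement does not bear on it.

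**Inputs from the documents.** Five readings per visit (Table 1: rest, last contraction, 5, 30 and 60 min); three visits, so 15 readings per participant; 50 participants with 15% dropout, 50 × 0.85 = 42.5, taken as 42 completers; α = 0.05.

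**Assumptions.** R = exercise SD divided by rest/recovery SD, range 1.5 to 3, with the rest/recovery residual SD set to 1. φ = share of the extra exercise variance (R² − 1) that is a stable trait of the person, recurring at each visit. Balanced data and otherwise independent residuals.

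**Formulas**, for training versus control at the same time point:

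- Pooled residual variance: V = 1 + (R² − 1) × [(1 − φ)/5 + φ × 2.4/14]. The 1/5 is one reading in five. A stable shift b at exercise leaves 0.8b at 3 readings and −0.2b at 12 after the random intercept absorbs b/5: 3 × 0.64 + 12 × 0.04 = 2.4, over 15 − 1 = 14 within-person df.
- Variance that matters: 1 at rest; 1 + (R² − 1)(1 − φ) at exercise, because the stable part cancels within person.
- r = model SE / true SE = √(V / variance that matters).
- Type I error = 2[1 − Φ(1.96 r)]. Power of a contrast that would have 80% with the right SE = Φ(2.80 − 1.96 r), where 2.80 = 1.96 + 0.84.

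Example, R = 2, φ = 0: V = 1 + 3/5 = 1.6. At exercise r = √(1.6/4) = 0.632 and type I error is 21.5%. At rest r = √1.6 = 1.265, type I error is 1.3%, and power is Φ(2.80 − 2.48) = 63%.

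| R | φ | V | Exercise: r, type I | Rest/recovery: r, type I | Power at rest |
|---|---|---|---|---|---|
| 1 | any | 1.000 | 1.000, 5.0% | 1.000, 5.0% | 80% |
| 1.5 | 0 | 1.250 | 0.745, 14.4% | 1.118, 2.8% | 73% |
| 1.5 | 0.5 | 1.232 | 0.871, 8.8% | 1.110, 3.0% | 73% |
| 1.5 | 1 | 1.214 | 1.102, 3.1% | 1.102, 3.1% | 74% |
| 2 | 0 | 1.600 | 0.632, 21.5% | 1.265, 1.3% | 63% |
| 2 | 0.5 | 1.557 | 0.789, 12.2% | 1.248, 1.4% | 64% |
| 2 | 1 | 1.514 | 1.231, 1.6% | 1.231, 1.6% | 65% |
| 3 | 0 | 2.600 | 0.537, 29.2% | 1.612, 0.2% | 36% |
| 3 | 0.5 | 2.486 | 0.705, 16.7% | 1.577, 0.2% | 39% |
| 3 | 1 | 2.371 | 1.540, 0.25% | 1.540, 0.25% | 41% |

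**Checks.** Simulation with 42 completers, three visits and five times, φ = 0, gives 14%, 22% and 29% at exercise and about 3%, 1.5% and 0.1% at rest for R = 1.5, 2 and 3, in line with the table.

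**With the plan's own gate.** Requiring a significant condition-by-time F test and then Bonferroni over five times (family size assumed), simulated false positives at exercise with φ = 0 are about 2%, 4% and 7%. With equal variances the same procedure gives under 0.5%.

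**Reversal.** At R = 0.5, V = (4 + 0.25)/5 = 0.85. At rest r = 0.922 and type I error is about 7%; at exercise r = √(0.85/0.25) = 1.84 and type I error is close to zero.

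**The case against.** The strongest reply has five parts.

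- **Direction.** No SD by time point appears anywhere, so larger spread at exercise is an expectation, not a documented fact. For BRS, or for HRV outcomes on the log scale, smaller spread cannot be excluded. This stands, and the point is therefore conditional on R.
- **False positives at exercise.** A reader might infer that this contrast simply runs at 15% to 30% error. The documents do not support that. It needs the extra spread to be visit-specific noise, whereas the comparison is a within-person cross-over; stable differences in reactivity cancel and leave the test conservative. It also ignores the gate and Bonferroni. This stands in full.
- **Scope.** A reader might extend the point to every main outcome. Cuff BP, FMD and cfPWV have no exercise reading, so their models are untouched. The sex contrast is between persons, its SE also carries the random-intercept variance, and the formula above does not cover it; no size is claimed for it.
- **Existing safeguards.** The Levene test is planned, but without a consequence. The log transformation reaches HRV only and is motivated by non-normality. Rerunning without outliers does not model unequal variance. These reduce the gap without closing it.
- **Software.** It would be too strong to say that lmerTest cannot accommodate this: an exercise-only random term at participant-by-visit level would add variance at that time point. The plan names no such term.

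**Conclusion.** The point holds for finger BP, RMSSD, HF, BRS and brachial blood flow. The firm part is at rest and in recovery: whenever exercise spread is larger, those training contrasts are too conservative, however the extra spread divides between person and visit. For R from 1.5 to 3, type I error is about 3% down to 0.2% and 80% power becomes about 73% down to 36% (74% down to 41% if the extra spread is wholly stable). At the exercise time point the documents do not determine even the sign of the error: 14% to 29% uncorrected in the visit-specific extreme, below 5% in the stable extreme, and about 2% to 7% in the visit-specific extreme after gating and Bonferroni. If R is below 1 the pattern reverses; only R near 1 leaves the model calibrated. All sizes rest on the assumed R, balanced data and independence within a visit. It is a change worth making before the data are analysed; it does not undermine the design.

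**What to change.** For outcomes with a during-exercise reading, state one of these as the main model:

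- residual variance that differs by time point (for example varIdent in nlme) **together with** a participant-by-time random effect;
- a parsimonious heterogeneous covariance in mmrm that lets exercise readings from different visits correlate on their own terms (fully unstructured over 15 readings would need 15 × 16/2 = 120 parameters, too many for about 42 completers);
- the planned model with robust standard errors clustered by participant and a small-sample correction.

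Time-specific variance with only the random intercept is not enough. If reactivity is stable, at R = 2 it would take the exercise variance as about 4 when only 1 matters for the contrast, giving an SE about √4 = 2 times too large, against 1.23 under the present plan.

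Keep the residual checks for sex and condition, and say what follows if they fail. Leave the cuff BP, FMD and cfPWV models as they are on this point.

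Cost: a few more variance parameters per model (four for variance by time, plus the random effect), a different R function or df method (nlme does not supply Satterthwaite df), and slightly wider intervals at some time points. No new data are needed, and little is lost if the variances prove equal.

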### Study Population

#### Eligibility criteria

##### Inclusion criteria

Eligible participants for this study are 1) persons with normal BP as defined by the American Heart Association (<130/90 mmHg) and ages between 18-40 years; 2) those with BMI < 30 kg/m^2; 3) persons with no cardiovascular risk factors and no clinically diagnosed cardiovascular disease; 4) persons recreationally active ( $\leq 2$  days of structured physical activity); and 4) able to speak and comprehend English.

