#### Number of Participants

We aim to sample 50 young healthy adults, 25 males, and 25 females.

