#### Recruitment methods

Recruitment will be conducted at the University of Massachusetts Boston and in the greater metropolitan Boston area. We will ask to place recruitment flyers at the University of Massachusetts Boston and to use the email services. Word of mouth will also be used as a recruitment strategy. All communication, including electronic and social media, will only be used to spread information about the study. Persons interested in this study will initiate contact via our study phone call line or the Integrative Human Physiology Laboratory email for further study details and subsequent screening for eligibility. We will only contact potential subjects as a follow-up to those who initiate contact with study personnel first. Prospective participants will be screened over the phone using the Physical Activity Readiness Questionnaire for Everyone (PAR-Q Plus), the International Physical Activity Questionnaire (IPAQ), and a health history questionnaire along with age, sex, and menstrual cycle regularity. To minimize coercion and undue influence on participants verbal and non-verbal/behavioral expressions will be used to assess possible objections or resistance to taking part in the study. At any time during the study, participants can withdraw without any negative consequences.

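### Age is collected but is in no model, so the sex main effect (not the within-person sex contrasts) carries any age gap between the men and women recruited

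*Combined protocol and SAP*

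**What the plan says.** All references are to the combined protocol and SAP.

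- **What is randomised (Research protocol).** "Participants will be randomly allocated to the isometric handgrip and the non-exercise training conditions". Only the training condition is allocated at random.
- **The sexes (Number of Participants).** "We aim to sample 50 young healthy adults, 25 males, and 25 females". No age matching, quota or stratification is described.
- **Age range (Inclusion criteria).** "ages between 18-40 years".
- **Age is available (Recruitment methods).** Telephone screening includes "a health history questionnaire along with age, sex, and menstrual cycle regularity". Recruitment is by flyers, email and word of mouth.
- **Model terms (Statistical analysis).** "Fixed effects will be set as time, sex, training condition", with a participant-level random intercept.
- **Covariates (Statistical analysis).** "MVC, %fat and free fat mass, and physical activity outcomes will be added to all linear mixed models as covariates". Resting heart rate and shear-rate AUC are added for particular outcomes.

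Age is in none of these lists. The same section estimates partial omega squared for every fixed effect and interaction, and runs post-hoc comparisons after significant ones. The sex main effect will therefore be estimated and interpreted alongside the interactions.

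**The concern.** The study's title is about sex effects, yet the comparison of men with women is observational. Randomising the training condition does nothing to balance age between the sexes. Resting blood pressure, arterial stiffness, endothelial function and autonomic indices can plausibly vary with age between 18 and 40. If the men and women recruited differ in age, part of that difference will be reported as a sex effect.

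The plan already accepts covariate adjustment. Several of its chosen covariates (MVC, fat percentage, fat-free mass) may partly be consequences of sex. Age cannot be caused by sex, so adjusting for it raises no question of removing part of the effect of interest.

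**Working it through.** **The plan's own figure.** The plan gives no number about age. Its nearest figure is N = 50 (Sample size: effect size 0.160, alpha 0.05, power 0.80, 15% dropout). Take 0.160 as Cohen's f in a within-between interaction, with 2 sexes, 6 measurement times and, as unstated assumptions, correlation 0.5 and no sphericity correction. The noncentral F calculation then gives 44. Dropout raises this to 44/0.85 = 51.8, or 52; multiplying instead gives 44 × 1.15 = 50.6, or 51. Both are close to 50. Nothing below depends on it.

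**Inputs from the documents.** 25 per sex, ages 18 to 40, SBP target difference 5 mmHg. All 25 per sex are used because a mixed model keeps the data already observed from participants who drop out.

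**Assumed inputs.** Age SD 5 to 6 years, SBP slope 0.2 to 0.6 mmHg per year, and age explaining 10% of between-person variance. The documents give none of these.

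**Step 1: age gap expected by chance.** SE of the difference in mean age = SD × √(2/25).

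| Age SD (years) | SE (years) | 95% limit, 1.96 × SE (years) | P(gap > 2 years) |
|---|---|---|---|
| 4 | 1.13 | 2.2 | 0.08 |
| 5 | 1.41 | 2.8 | 0.16 |
| 6 | 1.70 | 3.3 | 0.24 |
| 6.35 (uniform over 18–40, 22/√12) | 1.80 | 3.5 | 0.27 |

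**Step 2: shift in the sex main effect.** Shift = age gap × slope. For a 3-year gap this is 3 × 0.2 = 0.6 to 3 × 0.6 = 1.8 mmHg, or 12% to 36% of the 5 mmHg target.

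**Step 3: simulation.** 4,000 runs per setting, 25 per sex, true sex effect zero, 0.4 mmHg per year, age SD 5:

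| Nominal gap | Sex main effect without age | With age | SD of estimate, without → with age |
|---|---|---|---|
| 0 years | 0.02 mmHg | 0.04 mmHg | 2.47 → 2.43 |
| 3 years | 1.17 mmHg | 0.03 mmHg | 2.45 → 2.52 |
| 5 years | 1.90 mmHg | 0.01 mmHg | 2.45 → 2.72 |

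The shifts fall slightly below 3 × 0.4 = 1.2 and 5 × 0.4 = 2.0 because simulated ages were truncated to 18–40.

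**Step 4: within-person contrasts.** The sex-by-training contrast compares pre-to-post changes, so an additive age effect subtracts out. Simulated bias was −0.02 mmHg at a 3-year gap. If age changes the training effect by an assumed 0.1 mmHg per year, bias is 0.31 mmHg (3-year gap) or 0.47 mmHg (5-year gap). An age-by-training term reduces these to 0.03 and −0.03. An age main effect alone would not. The same reasoning applies to sex-by-time contrasts and an age-by-time term.

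**Step 5: precision.** SE factor = √(0.90 × VIF), where VIF = 1 + d²/4 and d = gap/SD.

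- No gap: √0.90 = 0.95, a 5% gain.
- 3-year gap at SD 5: d = 0.6, VIF = 1.09, factor √0.981 = 0.99, a gain of about 1%.
- 5-year gap at SD 5: d = 1, VIF = 1.25, factor √1.125 = 1.06, a loss of about 6%.

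**The case against.** The strongest reply is about scope. The plan's models address acute and training responses over time, and its sample size concerns differences over time and groups. The sex questions of most interest are therefore interactions, and an additive age effect cancels from those. This stands. A reader might infer from the omission that every sex finding, including sex-by-training, is confounded by age. The documents do not support that: participants are measured repeatedly and in both conditions, and nothing in the plan indicates that age modifies the response. What remains exposed is the sex main effect, which the plan also estimates and tests.

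Second, a chance gap is sampling variation that the unadjusted standard error already reflects on average. Systematic confounding would need recruitment that selects age differently by sex, whereas the plan describes the same channels for both. This also stands in part: an imbalance is a risk, not a known fact, and the documents give no figure for a gap beyond chance. Even so, once a particular sample has an age gap, its unadjusted contrast is not a comparison of men and women of the same age. Choosing to adjust only after seeing the gap would be a data-driven decision.

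Third, eligibility excludes hypertension, obesity, smoking and other risk factors, and fat percentage and activity are adjusted for. These may absorb some of an age difference, but they do not replace age.

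Finally, a reader might expect adjustment to tighten the sex estimate by about 5% as well as remove confounding. Step 5 shows that the two benefits do not come at full size together.

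**Conclusion.** The point holds for the sex main effect. Sex is an unmatched, observed factor across a 22-year age range, and a baseline variable already in hand is left out of every model. With 25 per sex and age SD 5 to 6 years (assumed), chance alone gives a gap above 2 years in about 16% to 24% of studies, with a 95% limit of 2.8 to 3.3 years. With SD 4 the figures fall to 8% and 2.2 years. A 3-year gap at 0.2 to 0.6 mmHg per year (assumed) moves the SBP sex main effect by 0.6 to 1.8 mmHg.

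The sex-by-time and sex-by-training contrasts are affected only if age modifies the response, and the assumed example gives a few tenths of a mmHg. The randomised comparison of training with control is not called into question. The benefit of adjustment is mainly less confounding. The precision gain is about 5% only if age is balanced by sex and explains 10% of between-person variance (assumed), and it shrinks or reverses as the gap grows.

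**What to change.** In Statistical analysis, before outcome data are examined:

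1. Add age in years, centred, as a fixed covariate in every linear mixed model.
2. Where a sex-by-time or sex-by-training interaction is interpreted, add the matching age-by-time or age-by-training term as a pre-specified sensitivity analysis. The age main effect alone does not protect these contrasts.
3. Report the age distribution separately for men and women, so that readers can judge any gap.

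The main term costs one between-participant degree of freedom. The sensitivity terms use further degrees of freedom, but only in the sensitivity models. No new data are needed, and N = 50 is unchanged. If the sexes do differ in age, the adjusted sex main effect will be somewhat less precise, which is the price of separating age from sex.
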